8.1.3 Protocol Deviations

Protocol deviations (as defined in the ZWI-ZW25-203 Monitoring Plan) will be identified by site monitors, the medical monitor and by checks of the clinical database. Protocol deviations will be classified into prespecified sub-types and categorized as either important deviations or non-important deviations. Important deviations are deviations that are considered significant. Important deviations will be summarized for each cohort. Per the study's COVID-19 deviation guideline, all deviations due to COVID-19 are documented on source documents and tracked in EDC. The frequencies of missed tumor scans and missed infusions due to COVID-19 will be provided.

8.1.4 Baseline Characteristics and Disease History

Baseline characteristics will be summarized using counts and percentages for categorical variables and summary statistics (mean, quartiles, standard deviation, and range) for continuous variables. Categorical variables listed in this section that are also identified as efficacy subgroups of interest ([Section 7.2](#)) will be summarized using the categories defined in that section. Characteristics to be summarized include the following:

- Demographic variables: age, sex, race and ethnicity (Hispanic, Non-Hispanic)
- Physical characteristics: height (cm), weight (kg)
- ECOG performance status

- Region or Country
- Disease history:
 - Primary disease (disease subtype)
 - Gallbladder cancer (GBC)
 - Intrahepatic cholangiocarcinoma (ICC)
 - Extrahepatic cholangiocarcinoma (ECC)
 - Stage at initial diagnosis (Stage I, II, ...IV and including substages e.g., IIb)
 - Duration (months) from initial diagnosis to metastatic/locally advanced
 - History of brain metastases (Yes, No)
 - Number of years since brain metastases was diagnosed
 - Tumor classification/characteristics
 - HER2 IHC tumor expression score (0, 1+, 2+, 3+, No result)
 - **Investigator** assessed tumor characteristics per RECIST 1.1.
 - Sum of diameters for target lesions (mm)
 - **ICR** assessed tumor characteristics per RECIST 1.1.
 - Measurable disease status (Yes, No)
 - Sum of diameters for target lesions (mm)
 - Prior radiotherapy
 - Any (Yes, No)
 - Total number of treatments
 - Prior cancer surgery
 - Any (Yes, No)
 - Total number of surgeries
 - Prior systemic anticancer therapy
 - Any (Yes, No)
 - Total number of regimens
 - Received Gemcitabine+Cisplatin
 - Prior systemic anticancer therapy for metastatic/locally advanced disease
 - Any (Yes, No)

- Number of regimens received
- Number of regimens received (<2, 2+)
- Received Gemcitabine
- Prior exposure to:
 - PD1 / PDL1 inhibitor
 - Gemcitabine monotherapy
 - Gemcitabine and Oxaliplatin in combination
 - Gemcitabine and Cisplatin in combination
 - Gemcitabine and Fluoropyrimidine in combination
 - Gemcitabine and other combination therapies
 - Fluoropyrimidine based therapies (without Gemcitabine)
- Baseline hepatic impairment (Per the National Cancer Institute Organ Dysfunction Working Group)
 - None
 - Mild
 - Moderate
 - Severe
- Baseline renal impairment (Per the Cockcroft-Gault formula for estimating creatinine clearance and FDA guidance titled: Pharmacokinetics in Patients with Impaired Renal Function - Study Design, Data Analysis, and Impact on Dosing and Labeling [September 2020])
 - Mild to moderate
 - Normal

8.1.5 Prior Systemic Anticancer Therapy, Radiotherapy and Surgeries

Prior systemic anticancer therapies will be coded using the World Health Organization Drug Dictionary (WHO-DD) Version 2009Q3 or higher and listed by ATC level 4 code. Prior surgery and radiotherapies will also be listed.

8.1.6 Concomitant Medications

Concomitant medications will be coded using the World Health Organization Drug Dictionary (WHO-DD) and listed and summarized by preferred term using counts and percentages. Multiple occurrences of the same medication within a subject will be summarized only once.

8.1.7 Concomitant Procedures

Concomitant procedures will be coded using the Medical Dictionary for Regulatory Activities (MedDRA) Version 24.0 or higher and listed and summarized by procedure and indication using counts and percentages. Multiple occurrences of the same procedure within a subject will be summarized only once.

8.2 Analysis of Efficacy

The primary efficacy analysis will be based on the Cohort 1 Efficacy Analysis Set. In addition, a pooled analysis combining Cohorts 1 and 2 may be presented. Additional analyses will be conducted on the Response Evaluable Analysis sets as described in [Table 4](#).

8.2.1 Best Overall Response

Best overall response (BOR) is defined as the best response observed per RECIST 1.1 from start of the study treatment until any of the following occurring for a subject:

- Receipt of non-protocol specified anticancer therapy
- Documented disease progression
- Death from any cause
- Subject withdrawal of consent

Confirmed BOR requires confirmation of CR or PR by a subsequent tumor assessment that is performed a minimum of 4 weeks from when the initial response is observed. See [Table 5](#) for more details.

BOR and confirmed BOR will be summarized using counts and percentages for both the ICR and investigator assessments. Confirmed best overall response will be determined as illustrated in [Table 5](#). Subjects who die and have no post baseline radiographic scans will be categorized as not evaluable (NE) for BOR and confirmed BOR ([Section 7.3.2](#)).

Concordance and discordance of ICR and investigator assessment of confirmed BOR will be summarized using counts and percentages.

Table 5: Determination of Confirmed Best Overall Response

First Time Point Response	Second Time Point Response	Confirmed Response (Best Response) *
PD	No further evaluation	PD
NE	PD	PD
CR	PD	SD or PD (1)
PR	PD	SD or PD (1)
SD	PD	SD or PD (1)
CR	CR	CR
CR	NE **	SD or NE (2)
PR	CR	PR
PR	PR	PR
PR	SD (3) **	SD
PR	NE **	SD or NE (2)
SD	CR	SD
SD	PR	SD
SD	SD	SD
SD	NE	SD or NE (2)
NE	CR	SD
NE	PR	SD
NE	SD	SD
NE	NE	NE

* A Best Response of SD can only be made after the subject is on-study for a minimum of eight (8) weeks (56 days) ± fourteen (14) days. If the subject is not on-study for this amount of time, any tumor assessment indicating stable disease before eight (8) weeks (56 days) will have a Best Response of NE unless PD is identified.

** Subsequent documentation of CR may provide confirmation of a previously identified CR for subjects where the second integrated response was NE. Subsequent documentation of PR may provide confirmation of a previously identified PR for subjects where the second integrated response was NE or SD. If the third TPR confirms the CR (or PR) then the Confirmed Response will be CR (or PR). For this study, only one (1) intervening NE is allowed between CRs/PRs. For example:

CR NE CR = CR; PR NE PR = PR. Additionally, one (1) SD is allowed between PRs (e.g., PR SD PR = PR). For this study, one (1) intervening NEs are allowed between CRs/PRs but one (1) intervening SD is allowed only between PRs. For example, CR NE CR = CR; PR NE PR = PR; CR SD CR ≠ CR; PR SD PR = PR.

Note: in the following scenario, PR SD NE PR, the second PR is not a confirmed PR.

(1) Best response will be SD if the first TPR is after eight (8) weeks (56 days) ± fourteen (14) days on-study. Otherwise, the best response will be PD.

(2) Best response will be SD if the first TPR is after eight (8) weeks (56 days) ± fourteen (14) days on-study. Otherwise, the best response will be NE.

(3) TPR is SD if the increase from the first to the second assessment does not qualify for PD.

Source Independent review charter, Version 1.0; Bioclinica: 03Aug2020

8.2.2 Objective Response and Confirmed Objective Response

Objective response is defined as achieving a BOR of CR or PR per RECIST 1.1. The proportion of subjects with an objective response and the corresponding two-sided, exact Clopper Pearson binomial 95% CI will be calculated for both the ICR and investigator assessments of disease response.

Confirmed objective response is defined as achieving a confirmed BOR of CR or PR per RECIST 1.1. The primary endpoint for this study is confirmed ORR based on the ICR response assessments. A secondary endpoint of confirmed ORR will also be computed based on the investigator response assessments. For each endpoint, the proportion of subjects with a

confirmed objective response and the corresponding two-sided, exact Clopper Pearson binomial 95% CI using the Clopper-Pearson method (Clopper 1934) will be calculated.

The time of first confirmed objective response is defined as the time from the first dose of study treatment to the earliest date a subject had a confirmed objective response (CR or PR). This will be summarized for subjects who had a confirmed CR or PR as follows:

- Descriptive statistics (n, mean, median, standard deviation, quartiles, range) of the time in weeks
- Cumulative percentage responding by Week 9, Week 17, Week 25, Week 33, Week 41, and after Week 41

Concordance and discordance of confirmed objective response per ICR and per investigator assessment will be summarized using counts and percentages.

8.2.3 Progression-Free Survival (PFS)

PFS is defined as the time from the first dose of study treatment to the date of documented disease progression (per RECIST 1.1) or death from any cause, whichever occurs first. Subjects who are alive and have not progressed at the time of the analysis will be censored at the time of their last tumor assessment that was a CR, PR, SD, or non-CR/non-PD. Details of the censoring scheme for this endpoint are described in [Table 6](#).

Kaplan-Meier plots and estimates of the quartiles and their corresponding two-sided 95% CI will be computed using the Brookmeyer and Crowley method (Brookmeyer and Crowley 1982) with log-log transformation (Collett 1994). The proportion of subjects with progression free survival at defined timepoints e.g., at 3, 6, 9 and 12 months will also be provided. Two-sided 95% CIs for these landmark PFS estimates will be based on the Greenwood estimator (Greenwood 1926).

Table 6: Censoring and Event Scheme for PFS

Scenario	Progression/Censor Date	Outcome
No baseline or no post-baseline response assessments and no death	Date of first dose	Censored
No disease progression (PD)	Date of last CR, PR, SD, or non-CR/non-PD	Censored
New anti-cancer treatment started before first PD	Date of last CR, PR, SD, or non-CR/non-PD on or prior to date of new anti-cancer treatment	Censored
Progressive disease (PD)	Date of PD, if response assessment prior to PD was either CR, PR, SD, or non-CR/non-PD	Progressed
	Date of last CR, PR, SD, or non-CR/non-PD, if PD occurred after 2 or more consecutive missed and/or NE overall response assessments*	Censored
Death	Death date, if last response assessment prior to death was CR, PR, SD, or non-CR/non-PD	Progressed

	and death occurred ≤ 18 weeks from the last response assessment	
	Death date, if there are no baseline or no post-baseline response assessments and death occurred ≤ 18 weeks from the first dose.	Progressed
	Date of last CR, PR, SD, or non-CR/non-PD, if death occurred after 2 or more consecutive missed and/or NE overall response assessments*	Censored
	Date of first dose, if there are no baseline or no post-baseline response assessments and death occurred > 18 weeks from the first dose	Censored

Note: * Two consecutive post-baseline tumor assessments refers to the next two protocol scheduled tumor assessments. Time is measured from the last adequate response assessment date. Subject will be considered to have missed two consecutive scheduled visits if no scans, scheduled or unscheduled, have occurred within the protocol-mandated disease assessment schedule; this will be within $2*(8 + 1) = 18$ weeks. Note: The scanning schedule is every 8 weeks.

Partial or missing dates of death dates, dates of last contact, and tumor assessment dates will be imputed as described in [Section 7.3.2](#). Separate PFS analyses will be presented for the ICR and investigator tumor assessments.

8.2.3.1 PFS Sensitivity Analyses

The following sensitivity analyses may be performed to assess the robustness of the estimates of PFS per ICR using the same statistical methods described in [Section 8.2.3](#) for the analysis of PFS.

- An analysis where clinical progression is treated as an event in addition to radiographic progression and death. Censoring rules per Table 6 and as stated in the below table will be followed..

Clinical progression	Clinical progression date, if last response assessment prior to clinical progression is CR, PR, SD, or non-CR/non-PD and clinical progression occurred ≤ 18 weeks from the last response assessment	Progressed
	Clinical progression date if there are no post-baseline, response assessments and clinical progression occurred ≤ 18 weeks from the first dose.	Progressed
	Date of last CR, PR, SD, or non-CR/non-PD, if clinical progression occurred after 2 or more consecutive missed and/or NE overall response assessments	Censored
	Date of first dose, if there are no baseline or no post-baseline response assessments and	Censored

	clinical progression occurred >18 weeks from the first dose
--	---

- An analysis in which subjects who initiate a new therapy prior to experiencing disease progression are considered to have had an event (PD) at the time of new therapy.
- An analysis where subjects who die or progress after 2 or more consecutive missed or non-evaluable tumor assessments are considered to have had an event (PD) on the date of the first missed visit.

8.2.4 Disease Control Rate (DCR)

Disease control is defined as a BOR of SD or confirmed CR or PR per RECIST 1.1. The proportion of subjects who achieve disease control and the corresponding two-sided, exact Clopper Pearson binomial 95% CI will be estimated for both the ICR and investigator assessments.

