9.4.6.4. Disease Control Rate

Disease control is defined as a best response of CR, PR, or SD per RECIST 1.1. The proportion of subjects who achieve disease control and the corresponding exact binomial 95% CI will be calculated.

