6.6 Timing of Analyses and Interim Analyses

No interim analyses of the efficacy will be performed for this study. The primary analysis of efficacy will be performed approximately 6 months after the last subject has been enrolled into Cohort 1.

Safety and study conduct will be monitored throughout the study by an independent data monitoring committee (IDMC). The committee is tasked with monitoring the safety of participants in this study through regular and/or ad hoc meetings. The first IDMC meeting will be held after the first 25 subjects have received at least 1 dose of study treatment; subsequent meetings will be held quarterly to review cumulative safety data to identify any potential new safety signals. Additional IDMC meetings will be held at least 28 days after the tenth subject enrolled in China has received 1 dose of zanidatamab to review safety. The IDMC will be responsible for making recommendations to the sponsor as to appropriate study direction; further details will be provided in the IDMC charter.

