8.2.5 Clinical Benefit Rate

Clinical benefit is defined as achieving SD for ≥ 24 weeks or a confirmed, BOR of CR or PR per RECIST 1.1. The proportion of subjects with clinical benefit and the corresponding two-sided, exact Clopper Pearson binomial 95% confidence interval will be calculated for both the ICR and investigator assessments.

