9 CHANGES IN THE PLANNED ANALYSIS

The following changes and/or clarifications to the analysis described in the study protocol are described.

Change	Reason for change

Definition of treatment-emergent adverse event (TEAE).
 
Protocol definition: “TEAEs are defined as events with an onset during or after receipt of the first dose of zanidatamab and up to and including 30 days after the last dose but prior to the start of a new anti-cancer therapy.”
 
SAP definition: “TEAEs are defined as AEs with an onset during or after receipt of the first dose of zanidatamab and up to and including 30 days after the last dose.”
	
The new definition in the SAP is more conservative than the definition in the study protocol.

Table 4: Analysis Set
 
Pharmacokinetics definition was modified to consider subjects who did not have a baseline sample
 
Immunogenicity analysis set definition was added
	
The new definition is more robust

Section 8.6: Pharmacokinetics Analysis
 
Definitions and analysis were added/clarified
	
Added clarification

Definition of PFS and DOR were updated to remove clinical progression as an event.
	
To align with standard definition of PFS

Definition of duration of response
	
Clarified compared to protocol language that response (PR, CR) must be confirmed.

Definition of disease control rate
	
Clarified compared to protocol language that PR and CR must be confirmed.

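### SAP 8.2.4 defines disease control through BOR without citing Table 5, so as written it drops unconfirmed responders; and Table 5's minimum for stable disease is not one cut-off

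*SAP*

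**What the plan says.** DCR by ICR and DCR by investigator are both listed as secondary endpoints (SAP 6.2). The protocol (9.4.6.4) has: "Disease control is defined as a best response of CR, PR, or SD per RECIST 1.1". The SAP (8.2.4) has: "Disease control is defined as a BOR of SD or confirmed CR or PR per RECIST 1.1". SAP Section 9 explains the change in one line: "Clarified compared to protocol language that PR and CR must be confirmed".

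The SAP keeps two response variables. Section 8.2.1 begins: "Best overall response (BOR) is defined as the best response observed per RECIST 1.1 from start of the study treatment". It then defines confirmed BOR separately, as needing a further assessment at least 4 weeks later, and sends the reader to Table 5 for that variable. Section 8.2.2 keeps the split: objective response uses BOR, while "Confirmed objective response is defined as achieving a confirmed BOR of CR or PR per RECIST 1.1". Section 8.2.4 uses the unqualified term and does not mention Table 5.

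Table 5 gives a result for pairs of successive time point responses. Its footnote * allows SD only after at least 56 days on study, with ± 14 days attached. The next sentence makes SD before 56 days NE unless PD is found, and repeats no tolerance. Notes (1) and (2) return to 56 ± 14 days. Scans have a ± 7-day window (SAP 6.1; Protocol 6.3.2.3).

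**The concern.** With BOR as the SAP defines it, one unconfirmed PR makes a subject's BOR equal to PR. That is not a BOR of SD, and it is not a confirmed PR, so 8.2.4 gives no disease control. A subject with SD, SD, SD counts and one with SD, SD, PR does not, so the better scan history scores lower. Table 5 and the protocol definition would each count both subjects.

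If 8.2.4 is tied to Table 5, as it should be, Table 5's SD minimum enters DCR, and a minimum with a plus-or-minus has no single value. Two programmers following the text faithfully could report different DCRs, for ICR and for investigator assessment alike.

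**Working it through.** **The plan's own figure.** The SAP states none for DCR. The interval method is the one used for ORR, so that was checked first: Clopper-Pearson for 23/75 gives 30.7% (20.5% to 42.4%), and 22/75 gives a lower limit of 19.4%. This agrees with SAP 6.5, where 23 is the minimum for a lower bound above 20%.

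**Part 1: unconfirmed responses.** Table 5 has 19 rows (patterns, not patients). Each was classified by the literal 8.2.4 wording and by Table 5's result. They can differ on 9 rows, all with a CR or PR not confirmed within the pair:

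| Pattern (first, second) | Literal 8.2.4 | Table 5 |
|---|---|---|
| PR-SD, SD-CR, SD-PR, NE-CR, NE-PR (5 rows) | no disease control | SD |
| CR-PD, PR-PD (2 rows) | no disease control | SD or PD, note (1) |
| CR-NE, PR-NE (2 rows) | no disease control | SD or NE, note (2) |

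A later scan may still confirm some of these; the difference concerns subjects in whom none does.

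Let c be the subjects with confirmed CR or PR, s those with a best response of SD, and u those with only an unconfirmed CR or PR whom Table 5 classes as SD. Take footnote * to apply to any best response of SD, so that s is the same under both readings.

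- Literal 8.2.4: (c + s)/N
- Table 5: (c + s + u)/N
- Difference: −u/N, which is 1/75 = 1.33 points per subject in Cohort 1 and 1/25 = 4.0 points in Cohort 2

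The documents do not give u. With an assumed 50 of 75 controlled under Table 5, DCR is 66.7% (54.8% to 77.1%). If u = 3, the literal reading gives 47/75 = 62.7% (50.7% to 73.6%). If u = 5, it gives 45/75 = 60.0% (48.0% to 71.1%).

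Unconfirmed responders are foreseeable: Protocol 6.5 asks for a scan at safety follow-up, if feasible, when the last one showed an unconfirmed PR or CR. Timing can add a few. The SAP says: "The primary analysis of efficacy will be performed approximately 6 months after the last subject has been enrolled into Cohort 1". As an illustration only, take that as exactly six calendar months, 181 to 184 days. A Week 24 scan falls 168 ± 7 = 161 to 175 days after first dose, and confirmation 28 days later falls at 189 to 203 days, past the cut-off. A last-enrolled subject with SD, SD and a first PR at that scan would be unconfirmed.

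**Part 2: the SD minimum.** Cycle 2 Day 28 is 28 + 28 = Study Day 56. With ± 7 days, the first scan may fall on Study Days 49 to 63, which is 15 days.

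| Minimum read as | In-window days that qualify | In-window days that fall short |
|---|---|---|
| 42 days (56 − 14) | 15 | 0 |
| 56 days, study day at least 56 | 8 (Days 56 to 63) | 7 (Days 49 to 55) |

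The counting unit also matters. Under SAP 7.7 study day is the date difference plus 1, so Study Day 56 is 55 elapsed days and would also fall short of 56 elapsed days. These are calendar days, not patients. They matter only in the 6 of 19 rows that use notes (1) or (2), where CR, PR or SD is followed by PD or NE. A pattern such as SD-SD is unaffected.

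**The case against.** The strongest reply is that the literal reading is strained. A BOR whose value is a confirmed CR or PR can only be the confirmed BOR. Table 5's result column heading begins "Confirmed Response (Best Response", so a BOR of SD can mean Table 5's SD, and Section 9 announces no exclusion of unconfirmed responders. This stands as evidence of intent: the documents do not support an inference that the sponsor meant to drop these subjects. It does not cure the text. BOR is a defined term in 8.2.1, and 8.2.5, one section later, writes "a confirmed, BOR of CR or PR per RECIST 1.1", so the SAP can attach the qualifier when it wants to.

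On the SD minimum, a reader might infer that footnote * contradicts itself with a flat 56-day rule. That goes too far: its second sentence opens by referring back to the stated amount of time, which can include the tolerance, and notes (1) and (2) repeat ± 14. Read as an ordinary visit tolerance, 42 days passes every in-window first scan. What remains is that the notes never state 42.

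A reader might also infer that the literal wording could raise DCR, by counting early SD without a minimum. The documents do not establish this, because footnote * is worded for any best response of SD. Nor do they show that the analysis date must produce unconfirmed responders: the interval is approximate, and the example covers only the last subjects enrolled.

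**Conclusion.** The point holds as a minor wording defect in two parts. Applied with the SAP's own terms, 8.2.4 omits unconfirmed responders whom Table 5 can class as SD and the protocol counts; the cost is 1.33 points of DCR per subject at N = 75 and 4.0 points at N = 25. Table 5's SD minimum can be read as 42 or 56 days, which changes the class of an SD or unconfirmed response on Study Days 49 to 55 when PD or NE follows.

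The sizes assume the planned cohort numbers. The number of subjects affected cannot be derived from the documents, and the independent review charter, which might settle the minimum, was not available. DCR is descriptive, no hypothesis is tested (SAP 6.4), and BOR and confirmed BOR are both tabulated, so much of the effect would be visible. A reader might infer that the primary endpoint is at risk. It is not: these choices move subjects only among SD, PD and NE, and leave confirmed CR and PR alone.

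**What to change.** In SAP 8.2.4, say that disease control means a confirmed BOR, determined by Table 5, of CR, PR or SD. In Table 5, footnote * and notes (1) and (2), replace the 56 ± 14 days and the bare 56 days with one SD minimum, in study days as defined in SAP 7.7. Set it no later than Study Day 49, the earliest in-window first scan, and reconcile it with the independent review charter. The cost is a few lines of SAP text and a check against the charter; no new data are needed.
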